Rationale: This endpoint is intended to ensure that women understand that this product is taken daily, without any breaks, and adhere to that instruction. The endpoint assesses whether users understand not to take breaks between pills as it is important that consumers do not miss several days in a row for any reason. It is being assessed in part because, some consumers may be accustomed to or familiar with the pattern of use for some combined oral contraceptives (COCs) where pills containing active ingredients are taken for 21 (or more) days followed by a pill-free break of 4-7 days (or 4-7 days of inactive pills). If a woman fails to heed the instructions not to skip pills, to take the product every day even if they bleed or have spotting, or to start the next pack the day after finishing a pack, and takes breaks in her use of the product, she may, if sexually active, put herself at risk of unintended pregnancy. Therefore, adherence to this message is designated as a primary endpoint. Please note that all cases of missed pills at any time will be captured in primary endpoint B above, so that this endpoint represents a special case in which multiple pills are missed in a row or pills are missed in between packs.

Secondary

A Actual Use: Proportion of user population who do not use study medication together

Do not use

with another form of hormone-containing birth control

• together with another birth control pill, vaginal ring, patch, implant, injection or an IUD (intra-uterine device)

Rationale: This endpoint measures whether subjects use the study product concomitantly with another hormone-containing birth control method. This is designated as a secondary endpoint for several reasons. While the concomitant use of a POP with another hormonal method of birth control or with an intrauterine device (IUD) is unnecessary, and would represent unnecessary expense, it is not unsafe. There would be no medical consequences of taking Opill[®] while using another contraceptive method since its concomitant use would not interfere with the efficacy of the other method or with the efficacy of Opill[®], and adding a relatively small dose of progestin to another method would be unlikely to alter the pattern of side effects of either method. Because failure to heed this message would not result in a safety concern or a reduction in efficacy, this endpoint is designated as secondary.

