9.3.1.2 Actual Use: Use of the study medication every day

This is adherence to the instruction to take one tablet every day, and is measured as the proportion of active dosing days among the user population (all subjects who take at least one dose of the IP) where a dose was taken (excluding days after a subject discontinues use of the IP—defined as the point at which no additional doses are taken). Specifically, to be included in the numerator (representing appropriate adherent use), a dosing day must meet one or more of the following criteria:

- 1. A tablet must be taken at some time during the dosing day.
- 2. Subject reports using a condom (or another barrier method) for any act of intercourse or abstaining from intercourse.

Regarding #2 above, the DFL provides explicit instructions for consumers when they miss pills which mitigate any risk of pregnancy related to that missed pill. So, while overall adherence to the daily dosing schedule will be presented as well (without accounting for secondary barrier method use for acts of intercourse or for abstinence), the overall measure of adherence will allow for those label-directed or appropriate consumer behaviors. Please note that for the purposes of this endpoint, diary data will serve as the primary source of data, with interview data collected by telephone used to supplement only in cases where diary data may be missing.

9.3.1.3 Actual Use: Use of the study medication at the same time of day

This endpoint is the proportion of active dosing days among the user population (all subjects who take at least one dose of the IP) which demonstrate adherence to the labeled directions for use related to the time of day the study medication is taken (excluding days after a subject discontinues use of the IP). Specifically, to be included in the numerator (representing appropriate adherent use), a dosing day must meet one or more of the following criteria:

- 1. For all dosing days where a tablet was taken the preceding day, the tablet is taken no later than 27 hours after the previous tablet (representing 24 hours from last dose plus three hours, consistent with the DFL instructions).
- 2. Subject reports using a condom (or another barrier method) for any act of intercourse or abstaining from intercourse.

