Again, regarding #2 above, the DFL provides explicit instructions for consumers when they are late taking their pill which mitigates any risk of pregnancy related to that late dose. So, while overall adherence to taking the product at the same time every day will be presented as well (without accounting for secondary barrier method use for acts of intercourse or for abstinence), the overall measure of adherence to dose timing will allow for those label-directed or appropriate consumer behaviors. Please note that for the

purposes of this endpoint, diary data will serve as the primary source of data, with interview data collected by telephone used to supplement in cases where diary data may be missing.

9.3.1.4 Actual Use: Use of the study medication without an extended break or any break between packs

While another endpoint measures all instances of any missed pills, this endpoint is intended to capture the special cases in which any subjects take an extended break from daily pill taking for any reason at any time, including. subjects who miss any pills between packs. For example, there may be subjects who do not appreciate the difference between a COC (where a medication break during menstruation is common) and the IP instructions which call for use daily without any breaks. This concept is measured as the proportion of the user population who do not take an extended break or a break between packs (where a single pack is defined as 28 tablets). A "break" is distinguished from discontinuation (defined above), which is a consumer choice not proscribed by the label.

The numerator will comprise the total user population minus those subjects who miss taking the IP for seven consecutive days on at least one occasion OR for four consecutive days or more on at least two occasions during active use of the product OR who take any break between packs (including missing one pill between packs), as recorded in their medication use diary. Subjects with a qualifying use pattern will be asked directly about that use during the next scheduled follow-up telephone interview. Please note that missed pills that are not included this endpoint are accounted for in another primary endpoint. Also note that for the purposes of this endpoint, diary data will serve as the primary source of data, with interview data collected by telephone used only to supplement in cases where diary data may be missing.

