9.3.2 Target Thresholds

Objective target thresholds will be set for all the primary endpoints. The objective will be considered met for these endpoints if the lower bound of the 2-sided 95% CI for each endpoint meets or exceeds the established threshold. Target thresholds and a summary of the associated rationale follow.

9.3.2.1 Self-Selection: Proportion of self-selection population who make a correct selection decision regarding use of the product.

HRA proposes to test this message as a primary endpoint because it is the self-selection phase of the study that will determine appropriate use of the product based on the DFL. This endpoint measures several relevant messages in the label:

Use:

For daily use by women to prevent pregnancy

Allergy alert: Do not use if you are allergic to this product or any of its ingredients. Do not use:

· f

if you are male

- if you have ever had any cancer
- if you are already pregnant or think you may be pregnant

This endpoint addresses both correct selection to use in order to prevent unintended pregnancy but also measures appropriate de-selection among individuals who should not use this product.

Do not use if you are male. This contraceptive pill is not intended for use by men. Use by a man would represent a fundamental misunderstanding of the product and its indication. Use by men is very unlikely: National Health and Nutrition Examination Survey (NHANES; 2011-2012) data showed no evidence of men of any age taking oral contraceptive pills³. However, if a man were to take a POP, it is unlikely to have serious clinical consequences. A variety of different progestogens, in a variety of doses and routes of administration, have been tested as hormonal contraceptives for men. Testosterone alone is effective but adding progestin results in an increased rate and extent of suppression⁴. High doses of progestins suppress endogenous production of gonadotrophins and testosterone thereby inhibiting spermatogenesis. Common side effects include acne and changes in mood and libido which are rarely severe enough to lead to discontinuation. Suppression of spermatogenesis is reversed when the treatment is stopped⁵.

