 - start having migraines with aura (headaches that start with changes in vision) or your migraine headaches get worse

Stop use and ask a doctor if you

- become pregnant
- develop yellowing of your skin or whites of your eyes (especially with fever, tiredness, loss of appetite or dark colored urine)

Keep out of reach of children. In case of overdose, get medical help or contact a Poison Control Center right away.

DFL Panel 3

Drug Facts (continued)

Directions

- take 1 tablet at the same time every day
 - this product will work best to prevent pregnancy when taken exactly as directed
 - you can start on any day of the month
 - use a condom (or another barrier method) every time you have sex during the first 2 days of use (48 hours) after you start your first pack of this product, because it takes 2 days for this product to start working
- never skip your daily tablet
 - to prevent pregnancy, take this product every day, even when you bleed or have spotting
 - when you finish this pack, start the next one the following day without a break
- if you are more than 3 hours late taking your tablet or miss taking your tablet on 1 or more days:
 - take 1 tablet immediately, as soon as you remember that you missed it
 - then go back to taking your daily tablet at your usual time
 - use a condom (or another barrier method) every time you have sex during the next 2 days (48 hours), because it takes 2 days for Opill® to start working again
- if you vornit for any reason or have severe diarrhea within 4 hours of taking your daily tablet, use a condom (or another barrier method) every time you have sex for the next 2 days (48 hours), because the medicine may not have been fully absorbed

Drug Facts (continued)

Other information

- as with any birth control method, this product does not prevent pregnancy all the time.
- this product will work best if you take it exactly as directed.
- read the instructions, warnings and enclosed product leaflet before use
- contains FD&C yellow No.5 (tartrazine) as a color additive
- store between 20°-25°C (68°-77°F).

Inactive ingredients

cellulose, FD&C Yellow No. 5, lactose, magnesium stearate, and polacrilin potassium.

Questions?

call 1-800-XXX-XXXX or visit www.xxxx.com

Carton including DFL

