18.2 Consumer Information Leaflet

CIL Table of Contents - Page 2

CIL Pages 3-5

How to Take Opili.

Take 1 tablet at the same time every single day (and no later than 3 hours from the time you took your pill the day before).

Never skip your daily pill.

- Never take a break between packs. When you finish one pack (all 28 pills), you should start the next pack the following day.
- Take Opill® every single day, even when you have your period, or if you have spotting or bleeding between periods.
- · Do not skip pills even if you do not have sex very often.

To start using Opill*:

- · You can start your first pack on any day.
- If you are switching from another birth control pill, vaginal ring, or patch, start taking Opill[®] the day after you stop the other method.
- You must take your daily pill at the same time of day every single day.
- You must use a condom (or another barrier method) every time you have sex during the first 2 days (48 hours).

What if I am late taking my pill?

Less than 3 hours late:

 Don't worry. Take 1 pill immediately and go back to taking your pill at your usual time the following day.

More than 3 hours late OR you missed one or more pills:

- Take 1 pill immediately, as soon as you remember.
- Then, go back to taking your pill at your usual time. This
 means you may take 2 pills in 1 day.
- For example, if you usually take your pill at night, but forget and remember in the morning, take 1 pill when you remember and take 1 pill again at the usual time that night.
- You must use a condom (or another barrier method) every time you have sex during the 2 days (48 hours) after you restart Opill*, because it takes 2 days to start working again.
- Take a pregnancy test or talk to a doctor if your period is late after missing any pills in the last month.

What if I vomit or have severe diarrhea within 4 hours of taking my pill?

- Use a condom (or another barrier method) every time you have sex for the next 2 days (48 hours) because the medicine may not have been fully absorbed.
- ---The next-day, take your daily-pill-at your usual-time.-

to Take Opill On Time

- Choose a convenient time of day. It is best to link this to something you already do at the same time every day. For example, when you wake up or when you brush your teeth.
- Set an alarm. Consider using your smartphone to set a daily alarm, and using the reminder stickers included in your pack.

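### Should the back-up-contraception credit in primary endpoints B and C be tied to the label's 48-hour window?

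*Protocol*

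**What the plan says.** Protocol 9.3.1.2 introduces endpoint B as a proportion of active dosing days among users ("all subjects who take at least one dose of the IP) where a dose was taken"). It then specifies the numerator: a dosing day counts if it meets at least one of two criteria. The first is that a tablet was taken that day. The second is "Subject reports using a condom (or another barrier method) for any act of intercourse or abstaining from intercourse". Section 9.3.1.3 uses the same second criterion for endpoint C, where the first criterion is a tablet no later than 27 hours after the previous one.

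The reason given for the credit in B is that "the DFL provides explicit instructions for consumers when they miss pills which mitigate any risk of pregnancy related to that missed pill"; 9.3.1.3 says the equivalent for late pills. Both sections also promise the adherence figure without any credit for barrier use or abstinence.

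The label instruction (Protocol 18.1) is to "use a condom (or another barrier method) every time you have sex during the next 2 days (48 hours"). The leaflet (Protocol 18.2) places the period "during the 2 days (48 hours) after you restart" the product.

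Elsewhere the protocol describes B as complete. The rationale for endpoint D in Table 1 (section 2.3) says "all cases of missed pills at any time will be captured in primary endpoint B above", and 9.3.1.4 says that "missed pills that are not included this endpoint are accounted for in another primary endpoint".

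Under Protocol 9.3.2 an objective is met "if the lower bound of the 2-sided 95% CI for each endpoint meets or exceeds the established threshold". The thresholds are 85% for B, 80% for C and 90% for D.

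SAP sections 1, 2 and 6.2.1 to 6.2.3 state that, because of early termination, only safety outcomes will be analysed. Of the planned endpoints, only secondary endpoint F (pregnancies) and other measure A (adverse events) remain.

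**The concern.** The credit rests on an instruction that the scoring does not check. The unit is the dosing day, so the natural reading of the second criterion is behaviour on that day, while the cited instruction looks 2 days ahead.

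For B, suppose a pill is missed on Monday with no sex that day, and tablets are taken on Tuesday and Wednesday with unprotected sex on both. Monday passes on the second criterion and the other days on the first: 3 of 3, although the label was not followed. For C, suppose Monday's dose is more than 27 hours after Sunday's with no unprotected sex on Monday, and Tuesday's dose is on time with unprotected sex on Tuesday: 2 of 2.

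The omission stands out because the protocol writes the window elsewhere. Secondary endpoint B covers the first 48 hours after starting, and other measure C the 48 hours after vomiting or severe diarrhea. The statements that B captures every missed pill also do not fit a score that counts some missed pills as adherent. Had B and C been tested, a score overstating label compliance could have met its threshold.

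**Working it through.** **Inputs from the documents.** Thresholds of 85% (B) and 80% (C), applied to the lower limit of an exact two-sided 95% interval (Protocol 9.3.2). Planned users: 720 (9.1). Missed pills (9.3.2.2): 1.0 to 1.2 per cycle by diary in the two studies whose methods are closest to this trial; 2.6 to 4.7 by electronic monitoring.

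**Assumption.** The documents give no rate of unprotected sex. Let q be the probability of unprotected sex on a day, independent of pill-taking and of other days, with q = 0.1, 2/7 and 3/7.

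**The plan's own figure.** The exact lower limit at 85% lies 2.50, 2.82, 3.18 and 7.16 points below the estimate for N = 900, 720, 576 and 135. This matches Table 5 (2.5, 2.8, 3.2, 7.2), read as the distance to the lower limit.

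**Score for B.** Let m be the share of days with a missed pill, and treat misses as isolated.

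- Without credit: 1 − m
- As written, same-day credit: 1 − m·q
- Credit only if there is no unprotected sex over k days: 1 − m·[1 − (1 − q)^k]. Here k = 2 is two days and k = 3 is the lapse day plus the next two.

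| Missed per 28 | Without credit | q | As written | k = 2 | k = 3 |
|---|---|---|---|---|---|
| 1.0 | 96.4% | 0.1 | 99.6% | 99.3% | 99.0% |
| 1.0 | 96.4% | 3/7 | 98.5% | 97.6% | 97.1% |
| 1.2 | 95.7% | 0.1 | 99.6% | 99.2% | 98.8% |
| 1.2 | 95.7% | 3/7 | 98.2% | 97.1% | 96.5% |
| 4.7 | 83.2% | 0.1 | 98.3% | 96.8% | 95.5% |
| 4.7 | 83.2% | 2/7 | 95.2% | 91.8% | 89.3% |
| 4.7 | 83.2% | 3/7 | 92.8% | 88.7% | 86.3% |

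From unrounded values, the fall from the written score is 0.3 to 1.7 points at 1.0 to 1.2 missed pills and 1.5 to 6.5 points at 4.7.

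**Against the threshold.** If the interval is computed with n = 720, B needs 631/720 = 87.6%. Only the last cell, 86.3%, falls short. Changing any one of its four conditions removes the reversal:

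- Window: k = 2 gives 88.7%, with a lower limit of about 86.1% to 86.2% at n = 720.
- Rate of unprotected sex: q = 2/7 gives 89.3%, above 87.6%.
- Missed pills: 1.2 gives 96.5%.
- Sample size: B is a proportion of dosing days. Treating all 720 × 112 = 80,640 days as independent, 85.25% is enough. Allowing for clustering within women, 86.3% reaches a lower limit of 85% from an effective n of about 2,730.

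**How low could pill-taking fall and still pass?** Let p be the share of days with a tablet (on time, for C) and S the score needed. Setting p + (1 − p)(1 − q) = S gives p = 1 − (1 − S)/q. At n = 720 and q = 2/7 to 3/7, B passes with tablets on 57% to 71% of days. C needs 598/720 = 83.1% and passes with 41% to 60% on-time days.

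For pill-taking that low, endpoint D also applies. It fails any subject who misses a pill between packs, has a 7-day gap, or has two gaps of 4 or more days. In a simulation of 112 days with independent misses and packs of 28 tablets, about 11% of subjects meet D at 57% pill-taking, 43% at 71% and 58% at 83%, against a 90% threshold.

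**The case for a change.** The best case for a change is that a primary endpoint should measure the behaviour used to justify it, whatever the size of the effect. Among missed days that the written rule credits, the share followed by unprotected sex within 2 days is 1 − (1 − q)², which is 49% at q = 2/7 and 67% at q = 3/7. The tablet-only and on-time-only figures are planned, but the credited score is the one called the overall measure. The diary holds dose times and each act of intercourse with the method used, so a windowed rule would cost little. The SAP blames the e-diary for the termination, not the endpoints, so the same definition could be carried into a repeat study.

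Most of this stands as a comment on the definition. The window is unstated, and the text around B is loose. Two things weaken it. The credit is described as covering label-directed or otherwise appropriate behaviour, which is wider than the 48-hour instruction alone. And every missed pill does appear in the uncredited figure, so the statements in Table 1 and 9.3.1.4 are imprecise but hide nothing. The reuse argument concerns a different study.

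**Conclusion.** The criticism is right on the text: the second criterion in 9.3.1.2 and 9.3.1.3 gives no window, and read naturally it does not test the 2-day instruction cited for it. No change follows, because there is nothing to gain in this trial. B and C will not be analysed, and the adverse-event and pregnancy summaries that remain do not use the criterion. A protocol amendment would alter no result or conclusion.

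Had the endpoints been analysed, the expected effect on B would have been small at diary-reported rates of missed pills (0.3 to 1.7 points) and moderate at 4.7 (1.5 to 6.5 points). It would have crossed 85% only with 4.7 missed pills, unprotected sex on 3 days a week, a three-day window and an interval based on 720 observations, all together. These sizes rest on an assumed rate of unprotected sex and on independence between days. The scenarios of very low pill-taking that still pass B would fail D by a wide margin under the same independence assumption.

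Anyone reusing the definition should note the missing window, and that the label and leaflet wording on when the 2 days begin would first have to be reconciled.

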3 STUDY DESIGN

This is an observational, open-label, multi-center, 16-week study designed to create as much as possible an OTC-like environment in which participants will make an initial self-selection and purchase decision about Opill® based only on their reading of the outside of the package including the DFL. Qualified participants who choose to do so will then

purchase the study medication, leave the study site and use the product on their own, guided by the OTC labeling. The study is designed to assess if, when and how subjects use the medication in an OTC-like environment.

It is important to note that none of the information gathered at screening, enrollment, or during the 16-week study period will be discussed with subjects until the End-of-Study interview.

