5.4.3.1 Week 4/8/12/16 Telephone Interview

Trained nurse interviewers will conduct the interim and end of study (EOS) interviews. Interim interviews will be conducted at week 4 (day 28 +/- 4), week 8 (day 56 +/- 4), week 12 (day 84 +/- 5), and week 16 (day 112 +/- 5). The intent of the monthly telephone interview is to collect information about use of the product, AEs and concomitant medications. Each interview will assess whether the subject has started taking the IP, and if so, collect information about how they have taken it. Questions will be designed to collect information about behaviors related to the use of the IP in a non-biasing and masked manner to avoid influencing future behavior (e.g. "Besides taking the medication, is there anything else you have done to prevent pregnancy since we last spoke?").

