5.4.3.2 End-of-Study Interview / Early Termination Interview

In most cases, the EOS interview will take place during the week 16 telephone contact, after the week 16 interim interview is complete. However, it is conceptualized as a separate interview in order to allow for collection of key end of study measures in cases where subjects elect to withdraw before the 16-week telephone call. The EOS interview will collect information from the subject regarding the use of other forms of contraception, and the timing of such use. This interview allows for direct questions about the rationale behind any behaviors that are not consistent with the DFL and CIL instructions, without concern about biasing the subject's subsequent behavior. Additional questions will be asked to include subject's experience with the study product, future contraceptive plans, and history and plans for interactions with a healthcare provider. Subjects will also be asked about possible pregnancy and will be asked to take the EOS self-administered pregnancy test, conducted at home, and record the results in their online medication use diary. Electronic reminders to complete and record the results of the self-administered home pregnancy test as well as schedule the EOS visit (described in Section 5.4.4 below) will be delivered every other day beginning at the day following completion of the use phase. Any subjects who do not report the results of their self-administered pregnancy test and also have not completed the end of study visit by 5 days after completion of the use phase will be contacted via telephone and asked to take the provided home pregnancy test and report those results by telephone, and to schedule an EOS visit.

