6.7 End-of-Study/Early Termination Telephone Interview

At the end of the study (typically this will be in conjunction with the 16-week call), or upon early termination from the study, all participants will be contacted via telephone by a trained nurse interviewer who will ask a series of questions related to the use of the study medication and the at-home, self-administered end of study pregnancy test results, as well as collect information related to concomitant medications and AEs.

As participation for that subject will then be complete, and therefore the risk of biasing future behavior irrelevant, this EOS interview will include direct questions about how the product was used. The answers to these questions will be part of the study database and used to determine the performance of some of the endpoints.

Typically, the EOS interview will be conducted during the 16-week telephone call immediately following the 16-week interim follow-up interview. However, in cases where subjects may withdraw or be withdrawn earlier for any reason, the EOS interview will be conducted by telephone at that time.

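### Asking users directly about a pill break at the week 4, 8 or 12 call conflicts with the protocol's masked-interview rule and could slightly raise primary endpoints B and C

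*Protocol*

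**What the plan says.** Endpoint D (protocol section 9.3.1.4) is scored per user. A user fails it if she misses seven days in a row once, misses four or more days in a row at least twice, or takes any break between packs, even of one pill. The diary is the primary source, and interview data only fill gaps in it. The section then adds: "Subjects with a qualifying use pattern will be asked directly about that use during the next scheduled follow-up telephone interview".

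Other sections set a different rule for the calls:

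- Section 5.4.3.1 has the questions on use at weeks 4, 8, 12 and 16 put "in a non-biasing and masked manner to avoid influencing future behavior".
- Section 5.4.3.2 says of the End-of-Study interview: "This interview allows for direct questions about the rationale behind any behaviors that are not consistent with the DFL and CIL instructions". The stated reason is that later behavior can then no longer be biased.
- Section 6.7 repeats this: with participation complete and "the risk of biasing future behavior irrelevant, this EOS interview will include direct questions about how the product was used".
- Section 3 states that "none of the information gathered at screening, enrollment, or during the 16-week study period will be discussed with subjects until the End-of-Study interview".

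Endpoints B and C use days, not users, as the unit. B is "measured as the proportion of active dosing days among the user population" (section 9.3.1.2). For C, "This endpoint is the proportion of active dosing days among the user population" (section 9.3.1.3). Both leave out only the days after a user discontinues.

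**The concern.** The protocol itself treats a direct question about off-label use as something that can change later use, and for that reason holds such questions back to the end. Section 9.3.1.4 nevertheless orders one during follow-up, and only for users already shown to have taken a break. A user who is asked about her break may take her pills more regularly afterwards. An OTC consumer would receive no such call.

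D cannot be improved this way, because a user with a true break has already failed it. B and C can, because her remaining active days stay in the numerator and denominator. At stake are the claim that use was guided by the labeling alone and, if the result is close, whether B or C meets its threshold.

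**Working it through.** **The plan's own precision figure.** Protocol section 9.1 gives ±2.8% around 85% at N = 720. The exact (Clopper-Pearson) interval for 612/720 runs from 82.18% to 87.53%. The lower half-width is 85.00 − 82.18 = 2.82, so the figure reproduces.

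**Margin needed to pass.** The rule in section 9.3.2 is that the lower 95% limit must reach the threshold. Treating 720 as independent units, for scale only:

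- B, threshold 85%: at least 631/720 = 87.64%, about 2.6 points above the threshold.
- C, threshold 80%: at least 598/720 = 83.06%, about 3.1 points above.
- D, threshold 90%: at least 664/720 = 92.22%, so at most 720 − 664 = 56 users flagged (7.8%).

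**Possible rise in B or C.** Rise = share flagged × share of days after the call × gain in daily adherence.

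- Share of days after the call, from the schedule in section 5.4.3.1 over 112 days: week 4, 84/112 = 0.75; week 8, 56/112 = 0.50; week 12, 28/112 = 0.25; week 16, none.
- Share flagged: not in the documents. Assumed 5% or 10%. At 10% the point estimate of D equals its 90% threshold.
- Gain: not in the documents. Assumed 5, 10 or 20 points.
- Also assumed: flagged and unflagged users contribute equal active days.

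Example: 0.10 × 0.50 × 0.20 = 1.0 point. All results are in percentage points:

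| Flagged | Call | Gain 5 | Gain 10 | Gain 20 |
|---|---|---|---|---|
| 5% | week 4 | 0.19 | 0.38 | 0.75 |
| 5% | week 8 | 0.125 | 0.25 | 0.50 |
| 5% | week 12 | 0.06 | 0.125 | 0.25 |
| 10% | week 4 | 0.38 | 0.75 | 1.50 |
| 10% | week 8 | 0.25 | 0.50 | 1.00 |
| 10% | week 12 | 0.125 | 0.25 | 0.50 |

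**Which rows are realistic.** A pack has 28 tablets, Day 1 is the day of dispensing, and the user chooses her own start date (section 5.3.3). At the first call, on day 28 ± 4, most users cannot yet have had a between-pack break. A flag at week 4 would mostly need one seven-day gap or two gaps of four or more days. The broad trigger therefore acts mainly from week 8, and the week 4 rows are the high end.

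**Cap if D passes.** With at most 56/720 flagged and a 20-point gain, the rise is at most 0.078 × 0.20 × 0.75 = 1.2 points at week 4, 0.8 at week 8 and 0.4 at week 12.

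**The case against.** The strongest reply is that the effect is unproven and probably small. Much of that stands:

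- The documents contain no data on whether such a question changes pill taking.
- A user whose only lapse is one pill per 28-tablet pack has at most 1/28 = 3.6 points to gain. Large gains are open only to the narrower group with long gaps.
- Missed or late days already count as adherent in B and C when the user abstains or uses a barrier method, which lowers the ceiling further.
- A break first flagged at the week 16 call does no harm, because the End-of-Study interview usually follows in the same contact.

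A second reply is that a prompt question has a use. It can help separate a missed diary entry from a missed pill while memory is fresh, and interview data do supplement D. This is fair, but section 5.4.3.1 already has every interim call collect how the product was taken, in masked form. That serves the purpose without singling out flagged users.

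A third reply is that nurses keep to a script (section 6.6), so the question could be worded neutrally and need not amount to discussing gathered information. Section 3 is for that reason the weaker part of the conflict. The conflict with sections 5.4.3.1, 5.4.3.2 and 6.7 remains, since the protocol orders a direct question and gives it no masked wording.

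**Conclusion.** The conflict between sections is plain in the text and does not depend on any assumption. The inflation of B and C is possible, not shown. With 5-10% flagged and a 20-point gain, the rise is 0.5-1.0 points if the question falls at week 8 and 0.25-0.5 at week 12, with 0.75-1.5 at week 4 as the high end. Against a passing margin of about 2.6 points for B and 3.1 for C, this is small, but it could tip a borderline result.

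A reader might infer a bias of several points by combining a wide flag share, a large gain and the earliest call. The documents do not support that combination: the broad trigger is mostly not yet active at week 4, the users it adds have little to gain, and D would already have failed. A reader might also infer that reported results were inflated. They were not: the study was stopped early over e-diary problems, and the SAP (sections 1 and 6.2.1 to 6.2.3) analyses only pregnancies and adverse events.

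**What to change.** Move the direct question about the break to the End-of-Study or early termination interview. At weeks 4, 8 and 12 ask all users the same masked questions on use, which can still fill gaps in the diary. Score D from the diary as planned. Inflation from this source is then zero by construction.

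If the interim question is kept, section 9.3.1.4 should state it as an exception to sections 3, 5.4.3.1, 5.4.3.2 and 6.7, and its neutral wording should be scripted. A sensitivity analysis of B and C should then censor flagged users' days after the first direct question.

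The cost is one sentence in the protocol and a script change. The downside is that reasons for a break are recalled later, by up to about 12 weeks (112 − 28 = 84 days) for one that would have been raised at week 4.
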